3.3. Study Definitions and Derived Variables

Dosing Periods

Dosing period may be described numerically (1, 2, 3, or 4) or in terms of the treatment received during the period (2 g zoliflodacin, 4 g zoliflodacin, placebo, or 400 mg moxifloxacin). Analysis of safety endpoints will be performed by treatment received for the period, not by the period number.

Period 1: From start of first Check-in day (Day -1) through the day before Check-in for the second dose, or ET Visit, whichever occurs first.

Period 2: From start of second Check-in day through the day before Check-in for the third dose, or ET Visit, whichever occurs first.

Period 3: From start of third Check-in day through the day before Check-in for the fourth dose, or ET Visit, whichever occurs first.

Period 4: From start of fourth Check-in day through Final Visit, or ET Visit, whichever occurs first.

Baseline

Baseline is defined for safety analyses as follows.

- Measurements prior to the first dose will not have a baseline defined.
- Measurements after the first dose, and prior to the second dose (including Period 2 check-in and pre-dose measurements and early termination measurements after the first dose and prior to the second dose) will use the last measurement prior to the first dose as baseline.
- Measurements after the second dose, and prior to the third dose (including Period 3 check-in and pre-dose measurements and early termination measurements after the second dose and prior to the third dose) will use the last measurement prior to the second dose as baseline.
- Measurements after the third dose, and prior to the fourth dose (including Period 4 check-in and pre-dose measurements and early termination measurements after the third dose and prior to the fourth dose) will use the last measurement prior to the third dose as baseline.
- Measurements after the fourth dose will use the last measurement prior to the fourth dose as baseline.

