Sequences will be referred to using these labels in TFLs. The four-letter codes for sequence indicate the order that the treatments will be given to the subject. For example, sequence CABD indicates that the subject would receive placebo in period 1, 2 g zoliflodacin in period 2, 4 g zoliflodacin in period 3, and 400 mg moxifloxacin in period 4.

Tolerability

Tolerability of zoliflodacin will be defined as follows. Tolerability will be concluded for a subject unless any one of the following occurred after receiving zoliflodacin as the most recent non-placebo dose: 1) subject discontinued study drug due to an AE, 2) subject choose to withdraw from the study due to an AE at any time from first dose of zoliflodacin until end of study, or 3) subject was withdrawn from the study by the investigator due to an adverse event at any time from first dose of zoliflodacin until end of study. Withdrawal or discontinuation of study drug after moxifloxacin as the most recent dose will not lead to a conclusion that zoliflodacin was not tolerable.

Visit and Time Point Names for Analysis of Safety and PK Endpoints

Analyses of clinical laboratory results, vital signs, ECG, and PK will be performed by planned time point, expressed as time in h relative to the most recent dose, within period. Labels for each time point are shown in [Table 1](#), including the order the time points will be shown in TFLs and abbreviated labels. The Max Severity Post-Baseline time point is a derived, conceptual time point used in tables displaying severity grading. All other time points refer to planned assessments per the protocol.

The “Follow-up” analysis time points refer to either Check-In visits for the next period (for analysis of treatments given in Period 1, 2, or 3) or to the Final Visit with Pre-dose 4 as baseline. For each treatment, if the treatment was given in Period 1, Period 2, or Period 3, then the pre-dose vital signs and ECG measurements prior to the next dose will be summarized. Listings will use protocol time point names rather

than analysis time point names, e.g. “Check-in” rather than “Follow-up” and “Pre-dose” rather than “Pre-dose (Prior to Next Dose).”

Table 1: Analysis Time Points for Safety and PK Endpoints

Order	Period	Analysis Time Point	Abbreviated Label	Endpoints	Baseline
1	1	Check-In	Day -1	Clinical Laboratory Results, Vital Signs, ECG	N/A
2	1	Pre-dose	0 h	Vital Signs, ECG, PK	N/A

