Only laboratory parameters reported as continuous values will be included in tables of summary statistics for change from baseline and in box plots for change from baseline. Because microscopic urinalysis evaluation is only performed in subjects with an abnormal urine dipstick result, urinalysis parameters assessed by microscopic evaluation will be excluded from tables of summary statistics for change from baseline and in box plots for change from baseline. However, urinalysis parameters assessed by microscopic evaluation will be included in summaries of toxicity grading, where the toxicity grade will be imputed as “Normal” for subjects where microscopic evaluation was not performed.

Laboratory parameters that have grading criteria for both decreases (result lower than normal range and baseline measurement) and increases (result higher than normal range and baseline measurement) will be summarized separately by direction of change. For example, sodium will be summarized separately as “Sodium, Decrease” and “Sodium, Increase.”

In tables summarizing toxicity grading, maximum severity observed for the parameter after dosing and within the same dosing period will be summarized (max severity post-baseline). Results of maximum severity for “Any Parameter” will be included for chemistry, hematology, and urinalysis laboratory results. For “Any Parameter” results, the maximum severity across all laboratory parameters in the respective category is summarized by time point, and from maximum severity post baseline.

By protocol, up to one repeat of a planned clinical laboratory assessment is allowed (*Laboratory values that are outside the range of eligibility but are thought to be due to an acute condition or due to collection or laboratory error may be repeated once.*). If replicates for clinical laboratory results are present in the database, then only the second replicate will be summarized and reported. Replicates not used in the analysis will not be listed.

Viral serology screening results ([Listing 12](#)), urine toxicology and alcohol screening results ([Listing 13](#)), and serum hCG (Human Chorionic Gonadotropin) pregnancy test results ([Listing 14](#)) will be listed. If FSH is measured for any subject during the study, FSH will be included in [Listing 14](#).

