9.7. Vital Signs and Physical Evaluations

Toxicity grade criteria for vital signs can be found in [Table 3](#). Unplanned vital signs measurements will be listed, but excluded from tabular and graphical summaries, except when calculating the maximum severity post-baseline.

Vital signs results will be listed ([Listing 15](#)).

Vital signs results will be summarized in tables and figures:

- Tabularly, by parameter, treatment, time point, and toxicity grade (including maximum severity post-baseline) ([Table 25](#))
- Tabularly, by summary statistics for change from baseline, reported by parameter, treatment, and time point ([Table 26](#))
- Graphically, using box plots showing the change from baseline by parameter, treatment, and time point ([Figure 39](#), [Figure 40](#), [Figure 41](#), [Figure 42](#), [Figure 43](#))

The following parameters will be presented (in order): Systolic Blood Pressure, Diastolic Blood Pressure, Heart Rate, Respiratory Rate, and Temperature

Vital signs parameters that have grading criteria for both decreases (result lower than normal range and baseline measurement) and increases (result higher than normal range and baseline measurement) will be summarized separately by direction of change.

In tables summarizing toxicity grading, maximum severity observed for the parameter after dosing and within the same period will be summarized (max severity post-baseline). Results of maximum severity for “Any Parameter” will be included. For “Any Parameter” results, the maximum severity across all vital signs parameters is summarized by time point, and from maximum severity post baseline.

The study protocol allows measurements of vital signs to be repeated in the case of an abnormal measurement. The following rules will be used to decide which measurement to include in summaries if more than one replicate was entered into the clinical database.

- If the first replicate is normal, then it will be used for analysis
- If the first replicate is abnormal, and the second replicate is also abnormal, then the first replicate will be used if has a severity equal to or greater to the second replicate, or the second replicate will be used if the second replicate has a higher severity than the first replicate.
- If the first replicate is abnormal, the second replicate is normal, and a third replicate measurement was not performed, then the first replicate will be used in the analysis.

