14.3.5 Displays of Laboratory Results

14.3.5.1 Chemistry Results

Table 20: Chemistry Clinical Safety Laboratory Results by Parameter, Maximum Severity, Time Point, and Dosing Period

[Implementation Note: If there is not at least 1 Mild, Moderate, or Severe Event for Any Period, Max Severity Post-Baseline, then only the Any Period, Max Severity Post-Baseline row will be shown for the parameter.]

Dosing Period	Time Point	N	Mild		Moderate		Severe	
			n	%	n	%	n	%
Chemistry - Any Parameter								
Any Period	Max Severity Post-Baseline	x	x	x	x	x	x	x
	24 h Post-dose	x	x	x	x	x	x	x
	Final Visit ^b	x	x	x	x	x	x	x
2 g Zoliflodacin	Max Severity Post-Baseline	x	x	x	x	x	x	x
	24 h Post-dose	x	x	x	x	x	x	x
	Follow-up ^a	x	x	x	x	x	x	x
4 g Zoliflodacin	Max Severity Post-Baseline	x	x	x	x	x	x	x
	24 h Post-dose	x	x	x	x	x	x	x
	Follow-up ^a	x	x	x	x	x	x	x
Placebo	Max Severity Post-Baseline	x	x	x	x	x	x	x
	24 h Post-dose	x	x	x	x	x	x	x
	Follow-up ^a	x	x	x	x	x	x	x
400 mg Moxifloxacin	Max Severity Post-Baseline	x	x	x	x	x	x	x
	24 h Post-dose	x	x	x	x	x	x	x
	Follow-up ^a	x	x	x	x	x	x	x
Chemistry – Sodium, Decrease								
Any Period	Max Severity Post-Baseline	x	x	x	x	x	x	x
	24 h Post-dose	x	x	x	x	x	x	x
	Final Visit ^b	x	x	x	x	x	x	x
2 g Zoliflodacin	Max Severity Post-Baseline	x	x	x	x	x	x	x
	24 h Post-dose	x	x	x	x	x	x	x
	Follow-up ^a	x	x	x	x	x	x	x
4 g Zoliflodacin	Max Severity Post-Baseline	x	x	x	x	x	x	x
	24 h Post-dose	x	x	x	x	x	x	x
	Follow-up ^a	x	x	x	x	x	x	x
Placebo	Max Severity Post-Baseline	x	x	x	x	x	x	x
	24 h Post-dose	x	x	x	x	x	x	x
	Follow-up ^a	x	x	x	x	x	x	x

Dosing Period	Time Point	N	Mild		Moderate		Severe	
			n	%	n	%	n	%
400 mg Moxifloxacin	Max Severity Post-Baseline	x	x	x	x	x	x	x
	24 h Post-dose	x	x	x	x	x	x	x
	Follow-up ^a	x	x	x	x	x	x	x
Chemistry – Sodium, Decrease								
...								

Note: The “Max Severity Post-Baseline” rows indicate the maximum severity experienced by each subject at any time point post baseline within the period, including unscheduled assessments. N=Number of subjects in the Safety Population that had clinical safety labs measured at the respective visit.

^a The “Follow-up” analysis time points refer to either Check-In visits for the next period (for analysis of treatments given in Period 1, 2, or 3) or to the Final Visit with Pre-dose 4 as baseline.

^b The “Final Visit” analysis time point uses the last measurement prior to the first dose as baseline.

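### Read literally, the Max Severity Post-Baseline row omits Follow-up results for treatments given in Periods 1 to 3 but includes them for Period 4, and the display note can then drop the Follow-up rows from the toxicity-grade tables

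*SAP*

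**What the plan says.** SAP 3.3 defines Period 1 as "From start of first Check-in day (Day -1) through the day before Check-in for the second dose" and Period 2 as "From start of second Check-in day through the day before Check-in for the third dose", with an earlier ET Visit closing either one. Period 3 follows the same pattern. Period 4 differs: "From start of fourth Check-in day through Final Visit, or ET Visit, whichever occurs first".

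SAP 3.3 also says what Follow-up means. These "analysis time points refer to either Check-In visits for the next period" when the treatment was given in Periods 1 to 3, or to the Final Visit when it was given in Period 4. The baseline rules treat the next check-in as a post-baseline record of the earlier dose: "Measurements after the first dose, and prior to the second dose (including Period 2 check-in and pre-dose measurements" use the last measurement before the first dose.

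For laboratory tests, SAP 9.6 restricts the maximum: "maximum severity observed for the parameter after dosing and within the same dosing period will be summarized". SAP 9.7 has the same rule for vital signs: "maximum severity observed for the parameter after dosing and within the same period will be summarized". SAP 9.8 gives no rule of its own for standard ECG, but the footnote to Table 28, like those to Tables 20 and 25, limits the maximum to time points within the period.

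The implementation notes to Tables 20, 25 and 28 add a display rule. If the Any Period maximum has no mild, moderate or severe event, "then only the Any Period, Max Severity Post-Baseline row will be shown for the parameter". Tables 22 and 24 repeat Table 20.

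**The concern.** A row labelled as the post-baseline maximum should cover every planned post-baseline result for the treatment. Under these definitions the next check-in falls between two windows. It comes after the earlier dose but outside that dose's period, and it lies inside the later period but before that period's dose. The same treatment row would then cover a shorter observation span for some subjects than for others.

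The display note adds to this. The check for an event looks only at the Any Period maximum. If that maximum leaves out Follow-up, a parameter with graded results only at Follow-up would appear in the toxicity-grade table as having none, and the rows holding those results would not be printed. Table 28 grades QTcF and PR prolongation, so the gap reaches a display that readers of a thorough QT trial will look at.

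**Working it through.** The plan states no figure to reproduce, so this is a check of windows against the visit schedule.

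**Inputs.** Check-in on Days -1, 8, 16 and 24, dosing on Days 1, 9, 17 and 25, and the Final Visit on Day 32 (Protocol 7.3, 7.4.2 and 7.6). Twelve sequences with six subjects each (SAP 3.3 and 4.1). Planned post-dose assessments from SAP Table 1: laboratory tests at 24 h and Follow-up; vital signs and standard ECG at 1, 2, 4 and 24 h, Follow-up, and Pre-dose (Prior to Next Dose) after Periods 1 to 3.

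**Windows from SAP 3.3 on nominal days.** A result enters a period's maximum only if it lies in that window and follows that period's dose.

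| Period | Window | Dose | Follow-up | In own period? | After the dose of the period it falls in? |
|---|---|---|---|---|---|
| 1 | Days -1 to 7 | Day 1 | Day 8 | No | No (falls in Period 2, dosed Day 9) |
| 2 | Days 8 to 15 | Day 9 | Day 16 | No | No (falls in Period 3, dosed Day 17) |
| 3 | Days 16 to 23 | Day 17 | Day 24 | No | No (falls in Period 4, dosed Day 25) |
| 4 | Days 24 to 32 | Day 25 | Day 32 | Yes | Yes |

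The pre-dose vital signs and ECGs on Days 9, 17 and 25 fail in the same way. A delayed dose moves the days but not the order, because check-in still precedes dosing.

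**Assessments per subject completing all four periods.**
- Laboratory: 4 at 24 h + 4 Follow-up = 8 planned. The 3 Follow-ups after Periods 1 to 3 are uncounted: 3/8 = 37.5%.
- Vital signs or ECG: 4 × 4 = 16 at 1 to 24 h, + 4 Follow-up + 3 pre-dose = 23 planned. Uncounted: 3 + 3 = 6, and 6/23 = 26.1%.

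The Final Visit is counted once here, as the Period 4 Follow-up.

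**Subjects per treatment.** Each treatment is last in 3 of the 12 sequences (for example, 2 g zoliflodacin in BDCA, CBDA and DCBA). So 3 × 6 = 18 subjects receive it in Period 4, and 72 − 18 = 54 (75%) receive it earlier.

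**Table 1 agrees.** Follow-up appears at orders 13, 25 and 37 under Periods 2, 3 and 4, with the earlier pre-dose as baseline. The maximum-severity rows for those periods (orders 15, 27 and 39) use the later pre-dose. The Listing 9 mock-up likewise files a Follow-up after 2 g zoliflodacin under Period 2, Day 8 (-1).

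**Suppression.** Suppose a chemistry parameter is graded only once, on Day 8 after a Period 1 dose. The maximum is none in Period 1 and none in Period 2. An Any Period row built from the period maxima is zero, so the treatment's Follow-up row with that one event is dropped. Table 20's Any Period block has no Follow-up row in which it could appear instead.

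**After the fix.** With a window from each dose to just before the next dose (or to the Final Visit), 8 of 8 laboratory and 23 of 23 vital-sign or ECG assessments fall in exactly one window, against 5 of 8 and 17 of 23 as written.

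**The case against.** The strongest reply is that the tables work by treatment, not by period number. SAP 3.3 says safety analysis is by treatment received, Tables 20, 25 and 28 place Follow-up inside each treatment's block, and post-dose records are attributed to the last treatment received. A programmer could reasonably include Follow-up on that basis. But SAP 3.3 offers the treatment label as another way of describing the same dosing period, with the same start and end. The attribution rule is applied there to AE summaries and listings and does not redefine the maximum. If inclusion was intended, the text contradicts it.

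Two replies stand in part. The SAP does not define the Any Period maximum separately, so the suppression step assumes it is built from the per-period maxima. Table 1's baseline column is also imperfect support, since it shows no baseline for the Period 1 maximum row.

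The replies about consequence stand in full. Suppression needs a parameter with no in-window graded result in any subject or period. A reader might infer that these abnormalities vanish from the report or that delayed effects go unreported. The documents do not support that:
- Protocol 7.3 has abnormal check-in assessments recorded as AEs, and Protocol 9.2.3 enters Grade 1 or higher laboratory abnormalities as AEs. SAP 9 assigns AEs to the preceding treatment.
- Tables 17 to 19 list every graded laboratory result. Listings 9 to 11, 15 and 17 hold the individual data.
- Tables 21, 23, 26 and 29 show Follow-up change from baseline with no suppression note, and the box plots add Follow-up. Urinalysis has no such display and relies on Table 19, Listing 11 and the AE tables.

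A reader might also infer a bias between zoliflodacin and placebo. The planned 54 to 18 split is identical for all four treatments, so the design gives no such bias.

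**Conclusion.** The point holds as a defect in a stated rule. On the SAP's literal definitions, the Max Severity Post-Baseline row mixes two observation windows and leaves out planned post-baseline results for 54 of 72 subjects per treatment. It can also trigger removal of the Follow-up rows that hold the only graded results for a parameter. The counts assume full enrolment and completion of the planned schedule. The suppression result further assumes that Any Period means the maximum over the four period windows.

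The reach is limited to the descriptive toxicity-grade tables (20, 22, 24, 25 and 28). AE reporting, the listings, the change-from-baseline displays and the primary QTcF analysis are not affected. It should be corrected before programming.

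**What to change.** Define the maximum-severity window by treatment: from each dose to just before the next dose, or to the Final or Early Termination Visit. State it once and apply it to laboratory tests, vital signs and standard ECG, amending SAP 9.6, 9.7 and 9.8 and the footnotes to Tables 20, 25 and 28 (22 and 24 follow Table 20). Say explicitly that the Any Period maximum is taken over these windows.

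Grade Follow-up after Periods 1 to 3 against that dose's pre-dose baseline, as SAP 3.3 already provides. The Final Visit needs a separate decision. SAP 3.3 says grading of change from baseline there uses the Period 1 baseline only, while the Table 20 footnote uses Pre-dose 4 when that visit serves as Follow-up. The two statements must be reconciled, or the new window will inherit the conflict.

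Change the display note so that a parameter's rows are suppressed only when no displayed time point has a graded result.

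The cost is SAP wording, revised table notes and a change to one derivation window. No new data are needed.
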